Diarrhea (12-20%) Dizziness (1-12%) Fatigue (48%) Nausea (48%) Headache (44%) Endometrial hypertrophy (38%) Hypokalemia (34%) Arthralgia (30%) Vomiting (26%) Peripheral edema (26%) Hypertension (24%) Dizziness (22%) Decreased appetite (20%) Abnormal thyroid test (18%) Xerostomia (18%) Back Pain (16%) Dyspnea (16%) Myalgia (14%) Pain (14%) Sinusitis (14%) Nasopharyngitis (12%) Extremity pain (12%) Diarrhea (12%)	Tachycardia Priapism Worsening of panic attack The frequency not defined
---	---

Adverse Effects: Adverse events (AEs) will be recorded and tracked for this protocol and will be reported to Brown University IRB and FDA. At the follow-up visit, AEs will be recorded and followed to resolution only if they are serious or unexpected, or if the study physician assesses them to be clinically significant. In accordance with FDA reporting requirements, all AEs occurring during the course of the study will be collected, documented, and reported by the investigators. The occurrence of AEs will be assessed starting on the day of randomization.

Unexpected Adverse Events: An unexpected AE is one that is not described with respect to nature, severity, or frequency in the current protocol.

Serious Adverse Events (SAEs): Each adverse event or reaction will be classified by a study physician as being serious or non-serious. Based on the seriousness of the adverse event or reaction, appropriate reporting procedures will be followed. The Code of Federal Regulations Title 21 part 312.32 and International Conference on Harmonization (ICH) Guideline for Industry: Clinical Safety Data Management: Definitions and Standards for Expedited Reporting, ICH-E2A March 1995, as implemented by the U.S. Food and Drug Administration, defines a SAE or serious adverse drug experience as any untoward medical occurrence at any dose that:

- results in death
- is life-threatening; (NOTE: The term "life-threatening" in the definition of "serious" refers to an event in which the subject was at risk of death at the time of the event; it does not refer to an event which hypothetically might have caused death if it were more severe)
- requires hospitalization or prolongation of existing hospitalization
- results in persistent or significant disability/incapacity; or
- is a congenital anomaly/birth defect

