- in 7 days if the SAE is unexpected, life-threatening or lethal, and at least possibly related to the investigational product, with a follow-up written report 8 days later
- in 15 days if the SAE is unexpected, but not immediately life-threatening
- in an annual report in all other cases

Follow-Up of All AEs/SAEs: All adverse medical events must be followed until they are resolved, or until all attempts to determine the resolution of the AE/SAE are exhausted. All outcomes and information regarding whether or not the subject was referred to their Primary Care Provider for additional follow-up must be recorded in the source document. Any SAEs and/or unexpected AEs among study participants during the follow-up period will be reported within 24 hours of knowledge of the event to the FDA, to our local IRB and to the Project Officer of this project via fax or phone call. All follow-up AEs will be recorded and followed to resolution only if they are serious, or if the study physician assesses them to be clinically significant.

Periodic Review of the Safety Data: Drs. [name] and [name] will meet prior to the enrollment of the first subject to review the research protocol, informed consent documents and plans for safety and data monitoring of the study. This review will determine the risks and benefits to research subjects, protection and safety of the subjects and offer suggestions for improving the study design. Moreover, Drs. [name] and [name] will meet in a regular basis during the duration of the study. These meetings will take place every 10 weeks for the entire duration of the study. 'Ad hoc' and/or emergency meetings will take place if needed for specific and/or safety reasons. Minutes of these meetings will be taken and filed in the regulatory binder of this project. The goals of these meetings will be to:

- (1) determine adherence to research plan
- (2) review interim analysis, if applicable, and determine specific data to be analyzed

- (3) evaluate end point/stop point rules
- (4) review protocol violations and deviations to assess adequacy of study
- (5) ensure documentation of informed consent
- (6) enrollment (followed eligibility criteria, enrollment numbers, visit compliance, screening failure information)
- (7) discuss investigator or key personnel changes
- (8) review completeness and quality of data collection forms, vital signs, clinical tests, and confidentiality

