Center Alcohol and Addiction Studies

Brown University

TITLE: A Pilot Study on the safety and efficacy of Mifepristone for the prevention of relapses of alcohol drinking

PI: [name]

NCT02243709

IND121984

DATE: December 15 2014

Statistical analysis

Distributional characteristics of outcome measures were examined to evaluate similarity to the normal distribution, detailed descriptive analysis of demographics, substance use, and clinical characteristics were conducted. Comparisons with these characteristics, in relation to enrolled versus completer status, were performed using *t*-tests to analyze continuous variables (e.g., age) and Chi square (χ^2) for categorical variables (e.g., sex, race, smoking status). Attrition rates between the screening visit and follow-up visit were examined descriptively to assess for potential bias. In addition, a logistic regression was performed to test for possible bias due to period (A/B: placebo first, then mifepristone and B/A: mifepristone first, then placebo) or medication carryover (1: placebo and 2: mifepristone), as done in our prior cross-over trial¹.

Primary outcomes: safety and tolerability of oral administration of mifepristone was assessed after 7 days in outpatient setting, and when it was administered with yohimbine and alcohol during the laboratory paradigms. These analyses included comparing the number of adverse events (AEs) between the mifepristone and placebo condition via a χ^2 test. The results were presented using summary statistics such as number of subjects (*n*); mean (*M*); standard deviation (*SEM*) or frequency distributions (%).

Primary outcomes: safety and tolerability assessed by the number of adverse events (AEs) of oral administration of mifepristone was assessed after 7 days in an outpatient setting, and when it was administered with yohimbine and alcohol during the laboratory paradigms. Additional safety and tolerability analysis included hemodynamic response, alcohol pharmacokinetics, and subjective effects of alcohol between the mifepristone and placebo condition (χ^2 test).

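### The protocol contradicts itself on which adverse events are recorded at follow-up, and protocol and SAP do not fix one window for counting them

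*Protocol*

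**What the plan says.** In the protocol's Adverse Events section, the Adverse Effects paragraph restricts what happens at follow-up: "At the follow-up visit, AEs will be recorded and followed to resolution only if they are serious or unexpected", with a further allowance for events that the study physician considers clinically significant. The following sentence has no such filter: "all AEs occurring during the course of the study will be collected, documented, and reported by the investigators". The paragraph also gives a start, "The occurrence of AEs will be assessed starting on the day of randomization", but no end.

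The later paragraph Follow-Up of All AEs/SAEs opens with "All adverse medical events must be followed until they are resolved" (or until attempts to establish resolution are exhausted). It then says "Any SAEs and/or unexpected AEs among study participants during the follow-up period will be reported within 24 hours of knowledge of the event". It closes with "All follow-up AEs will be recorded and followed to resolution only if they are serious", or clinically significant in the study physician's view. Unexpected events are not in this second list.

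On the outcome, the SAP describes the primary outcome as "safety and tolerability assessed by the number of adverse events (AEs"), and both of its statements of that outcome place the assessment after seven days of outpatient dosing and during the laboratory sessions. The protocol's Data analysis section instead compares the number and intensity of events by week as well as in the laboratory sessions, on a scale that includes mild events.

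**The concern.** Safety and tolerability are the primary aim, and the number of adverse events is the primary measure. A recording rule that depends on the visit, and that one sentence imposes while the next removes, leaves staff to decide what is written down. The restrictive wording is also selective in kind. The protocol defines the term thus: "An unexpected AE is one that is not described with respect to nature, severity, or frequency in the current protocol". A non-serious event that matches the side-effect table, such as nausea, headache or fatigue, is therefore expected, and at follow-up it would be recorded only if a physician judged it significant.

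Two things are at stake: a complete account of tolerability after each week of dosing, and a count that means the same thing in both documents.

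**Working it through.** The plan states no figure to reproduce, and the SAP's Power section gives no event rate behind N=20 or N=32. The check is therefore mainly a comparison of texts.

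**1. The rules side by side**

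- Adverse Effects, first rule: at follow-up, record if serious, unexpected or clinically significant.
- Adverse Effects, second rule: collect and document all events during the study.
- Follow-Up of All AEs/SAEs, first rule: follow all events until resolved.
- Same paragraph, last rule: record and follow follow-up events only if serious or clinically significant.

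The first two conflict on recording. The last two conflict on following to resolution. The two restrictive lists also differ: an unexpected, non-serious event at follow-up is recordable under one and not under the other, although it must be reported within 24 hours.

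**2. Which visits.** The section Visits 4 and 6 (Follow-up) gives that name to both. With 7 days of dosing and a 30-day washout, the second laboratory session falls on day 7 + 30 + 7 = 44, which matches the protocol's Days 7 and 44. Each condition is thus followed by one follow-up visit. Visit 4 is also where second-period medication is dispensed. A mild first-period event still present then, if not recorded, could later be attributed to the wrong condition.

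**3. Which window**

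- SAP, read strictly: events elicited after seven days and in the laboratory (Visits 3 and 5). The follow-up filter does not reach these.
- SAP, read by date of onset: an event from the dosing week first mentioned at Visit 4 or 6 belongs to the count and could be lost.
- Protocol, Data analysis: a weekly comparison. Dosing lasts about one week per condition, and the scheduled weekly calls fall in washout and follow-up, so this can include the follow-up weeks.

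**4. Illustrative size.** Let f be the share of counted events first reported at follow-up and m the share of those filtered out. The under-count is f × m. Both inputs are assumptions; take m from 50% to 90%.

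- f = 0 (strict SAP window): 0%.
- f = 10%: 5% to 9%.
- f = 25%: 12.5% to 22.5%.
- f = 50%: 25% to 45%.

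**5. Effect on the comparison.** Assume 2 on-treatment events per participant on mifepristone and 1 on placebo, plus 0.5 and 0.25 at follow-up. The true ratio is 2.5/1.25 = 2.0.

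- 20% of follow-up events kept in both conditions: (2 + 0.1)/(1 + 0.05) = 2.0, unchanged.
- 20% kept on mifepristone, 50% on placebo: 2.1/1.125 = 1.87. With follow-up events doubled to 1 and 0.5: 2.2/1.25 = 1.76.
- The reverse, 50% and 20%: 2.25/1.05 = 2.14.

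The equal filter is neutral here because follow-up events have the same ratio as on-treatment events. With 0.5 follow-up events in each condition, the true ratio is 2.5/1.5 = 1.67, and keeping 20% of both gives 2.1/1.1 = 1.91. The direction is therefore open.

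**The case against.** The strongest reply is that the primary count is untouched. Both SAP statements of the primary outcome name the seven-day dosing week and the laboratory sessions, and neither names Visit 4 or 6. On a strict reading this stands in full.

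Other text also favours complete capture. The synopsis has adverse events assessed at each visit, the Protections Against Risks section has them systematically evaluated and recorded, and weekly calls are planned. The visit schedule and side-effect form are in appendices not available here. The authors may also have meant to limit only follow-up to resolution. That is plausible, but the sentences as written limit recording too. The singular in the first rule might mean Visit 6 alone; the heading for Visits 4 and 6 points the other way.

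A reader might infer that the combination will look safer than it is. The documents do not support this. Mifepristone, yohimbine and alcohol are taken together under study conditions only at Visits 3 and 5, where no filter applies. The same rule follows both conditions, and unequal loss is an assumption.

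A reader might also note that follow-up occupies 30 of 37 days, or 81%, of each period. That is calendar time off drug, not a share of events. The 44% to 48% side-effect rates in the protocol's table are not rates of events first reported a month after dosing, and another part of the same table gives headache as 2-31%.

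**Conclusion.** The contradiction is established from the text alone: two paragraphs each contain rules that cannot both be followed, and their restrictive lists differ on unexpected events. It is also established that protocol and SAP do not give one counting window.

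Under-counting is a possibility, not a finding. It arises only if the weekly comparison includes the follow-up weeks, or if events from the dosing week or laboratory session first surface at Visit 4 or 6. Its size is 0% on the strict SAP window and 5% to 45% under the assumed f and m. The effect on the between-condition comparison could be nil or go either way. The point still merits correction, because the restrictive rule, if followed, discards non-serious expected events in a study whose first aim is tolerability.

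**What to change.** In the protocol's Adverse Events section, state one rule: every adverse event of any severity is recorded at every visit and telephone contact from randomization to Visit 6. Let any restriction apply only to how long non-serious events are followed. Make Adverse Effects and Follow-Up of All AEs/SAEs agree, including on unexpected events.

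In the protocol's Data analysis section and the SAP's primary outcome, define the same counting window (start, end, and whether onset or report date governs) and the same rule for attributing an event to a period, including events ongoing at Visit 4.

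The SAP is written in the past tense. If data are already collected, the sponsor should state which recording rule was applied and tabulate events by visit and condition.

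The cost is protocol and SAP wording and a few more form entries at follow-up contacts.

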Center Alcohol and Addiction Studies

Brown University

TITLE: A Pilot Study on the safety and efficacy of Mifepristone for the prevention of relapses of alcohol drinking

PI: [name]

NCT02243709

IND121984

DATE: December 15 2014

Statistical analysis

Distributional characteristics of outcome measures were examined to evaluate similarity to the normal distribution, detailed descriptive analysis of demographics, substance use, and clinical characteristics were conducted. Comparisons with these characteristics, in relation to enrolled versus completer status, were performed using *t*-tests to analyze continuous variables (e.g., age) and Chi square (χ^2) for categorical variables (e.g., sex, race, smoking status). Attrition rates between the screening visit and follow-up visit were examined descriptively to assess for potential bias. In addition, a logistic regression was performed to test for possible bias due to period (A/B: placebo first, then mifepristone and B/A: mifepristone first, then placebo) or medication carryover (1: placebo and 2: mifepristone), as done in our prior cross-over trial¹.

Primary outcomes: safety and tolerability of oral administration of mifepristone was assessed after 7 days in outpatient setting, and when it was administered with yohimbine and alcohol during the laboratory paradigms. These analyses included comparing the number of adverse events (AEs) between the mifepristone and placebo condition via a χ^2 test. The results were presented using summary statistics such as number of subjects (*n*); mean (*M*); standard deviation (*SEM*) or frequency distributions (%).

Primary outcomes: safety and tolerability assessed by the number of adverse events (AEs) of oral administration of mifepristone was assessed after 7 days in an outpatient setting, and when it was administered with yohimbine and alcohol during the laboratory paradigms. Additional safety and tolerability analysis included hemodynamic response, alcohol pharmacokinetics, and subjective effects of alcohol between the mifepristone and placebo condition (χ^2 test).

Secondary outcomes: Craving measures included alcohol craving questionnaire short form-revised (ACQ-SF-R)². Values of the water trials for each dependent variable were inserted as covariate in the model (allowed for the dependent variable to be specific for alcohol), time coded: t_1 =alcohol trial 1 and t_2 =alcohol trial 2. In the bar laboratory, alcohol consumption was measured by number of drinks consumed (*t*-test). In the outpatient setting, alcohol consumption was measured by self-report using the timeline follow back method, reported as heavy drinking days and drinks per week.

All statistical analysis was performed after participants had their follow-up visit and the study database had been locked. All the statistical procedures were performed by IBM SPSS Statistics for Windows, version 27 with Macro MEMORE extension⁹ (IBM Corp., Armonk, NY, USA) and GraphPad Prism (v.5) was used to generate figures (La Jolla, CA, USA). The effect sizes were calculated as η^2 for GLM and Cohen *d* for *t*-test. All statistical tests were two-tailed, and statistical significance was accepted if an alpha value $p<.05$ was obtained.

For all outcomes, we utilized an intention-to-treat (ITT) approach, where participants were examined based on their *a priori* randomized protocol and received at least one dose of the study medication

(mifepristone or placebo)³. All analyses were conducted using Generalized Estimating Equations (GEE)⁴ with robust standard errors, and an unstructured correlation matrix, unless noted.

Power

This was a proof-of-concept trial to demonstrate the feasibility of the combined study design, the safety and tolerability of mifepristone and yohimbine while consuming alcohol, and the potential value of testing mifepristone in an appropriately-powered larger RCT. In selecting a target sample size, we balanced power considerations and feasibility given the translational nature of this trial. Because of the within-subjects design, power to test the effects of study drug is optimized for this modest sample size (originally $N=20$ then, after additional funding, increased to $N=32$). For the safety and tolerability outcomes (primary) adverse events difference was detected based on a judgement concerning the minimal effect which has clinical relevance in the management of patients. In a noninferiority trial, the exact sample size cannot be fixed in advance because it depends upon the chosen stopping guideline⁵.

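### The SAP's period check codes treatment sequence rather than period, its carryover code and dependent variable are not explained, and the laboratory drinks t-test names no period term

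*SAP*

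**What the plan says.** The protocol (Overview of Proposed Research) describes a randomised, double-blind crossover with two dosing weeks and a washout of about a month. The laboratory sessions are Visits 3 and 5, and the follow-ups are Visits 4 and 6.

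The SAP's first section, Statistical analysis, says that "a logistic regression was performed to test for possible bias due to period (A/B: placebo first, then mifepristone and B/A: mifepristone first, then placebo"). The same sentence gives the regression a second target, worded as "or medication carryover (1: placebo and 2: mifepristone"). It adds that this follows the authors' prior crossover trial, which is cited but not reproduced. The sentence just before it reads "Attrition rates between the screening visit and follow-up visit were examined descriptively to assess for potential bias".

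The SAP's outcome analyses are:

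- **Adverse events:** "These analyses included comparing the number of adverse events (AEs) between the mifepristone and placebo condition via a" chi-square test.
- **Other safety measures:** a chi-square test is also named for "hemodynamic response, alcohol pharmacokinetics, and subjective effects of alcohol between the mifepristone and placebo condition".
- **Craving:** "Values of the water trials for each dependent variable were inserted as covariate in the model". The time factor in that model is alcohol cue trial 1 against trial 2 within one session.
- **Laboratory drinking:** "In the bar laboratory, alcohol consumption was measured by number of drinks consumed", with a t-test.
- **Outpatient drinking:** "reported as heavy drinking days and drinks per week".
- **Default method:** GEE unless noted, with no list of fixed effects.

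The protocol's Data analysis section names paired t-tests for medication effects, ANCOVA with trauma, stress and anxiety covariates, and repeated-measures ANOVA for consumption. It states no period term either. It also wants an effect size from which to plan later studies, and the SAP uses Cohen d for t-tests.

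**The concern.** In a two-period, two-treatment crossover, sequence, period and treatment are different factors. The SAP gives the name of one to another. A reader who sees that a period or carryover test was run and found nothing could take it that session order had been ruled out as an influence on craving, drinking or adverse events. The check as described does not support that.

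Period matters most for a plain comparison of the two drug conditions. Participants may drink differently at their second bar session simply because it is the second. If the analysis has no period term, that shift goes into the error. If the two sequences also differ in size, part of it goes into the estimated drug effect. Carryover is a live question here because the protocol (Visits 4 and 6) looks for an effect of mifepristone that outlasts dosing.

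**Working it through.** **1. What the factors can test.** Write the four cells as sequence by session:

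| Sequence | Visit 3 | Visit 5 |
|---|---|---|
| A/B | placebo | mifepristone |
| B/A | mifepristone | placebo |

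A/B against B/A does not change within a participant, so as a main effect it cannot contrast Visit 3 with Visit 5. For the 1/2 code there are two natural readings. If it means the current drug, it is the treatment factor. If it means the first-period drug, it repeats sequence.

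In terms of the four cell means, intercept + period + treatment has rank 3, and adding sequence gives rank 4. Adding preceding-treatment carryover as well leaves rank 4, so carryover and sequence-group differences cannot be separated.

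**2. What a missing period term would do to the drinks t-test, if it is paired.** The documents give no SD, effect size, period shift or numbers per sequence, so there is no plan figure to reproduce.

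*Inputs:* N=32 (SAP, Power); two-sided 5% (SAP). *Assumed:* SD of the within-person difference = 1; period shift δ of 0.25, 0.5 or 1.0 of that SD; splits of 16/16, 18/14 and 20/12.

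*Model:* the mifepristone-minus-placebo difference has mean τ+δ in A/B and τ−δ in B/A.

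*Reference effect:* 80% power for a paired t-test with n=32, 31 df and no shift gives τ = 0.511 (noncentral t).

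*Bias of the unadjusted mean difference:* δ(nAB − nBA)/32. At 20/12 and δ=0.5 this is 0.5 × 8/32 = 0.125 SD.

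*Paired d at 16/16:* τ/√(1 + δ²·32/31).
- δ=0.25: 0.511/√1.0645 = 0.50
- δ=0.5: 0.511/√1.2581 = 0.46
- δ=1.0: 0.511/√2.0323 = 0.36

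*Type I error and power of the unadjusted test, by simulation:*

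| Split | δ | Bias (SD) | Type I error | Power |
|---|---|---|---|---|
| 16/16 | 0.25 | 0 | 4.4% | 78% |
| 16/16 | 0.5 | 0 | 2.9% | 73% |
| 16/16 | 1.0 | 0 | 0.6% | 50% |
| 18/14 | 0.25 | 0.03 | 4.7% | – |
| 18/14 | 0.5 | 0.06 | 3.9% | – |
| 18/14 | 1.0 | 0.125 | 2.0% | – |
| 20/12 | 0.25 | 0.06 | 5.6% | – |
| 20/12 | 0.5 | 0.125 | 7.0% | 90% or 47% |
| 20/12 | 1.0 | 0.25 | 8.7% | – |

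The two power values at 20/12 depend on which sequence is the larger.

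**3. The same comparison with a period term.** The estimate is the average of the two sequence means, with standard error √[(1/nAB + 1/nBA)/4] and 30 df. The shift cancels at every split, so bias is 0 and type I error is 5.0%. With no shift, power is 79.9% at 16/16, 79.3% at 18/14 and 77.3% at 20/12, against 80.0% for the unadjusted test.

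**4. How likely unequal sequences are.** Under simple 1:1 randomisation of 32 (assumed), the binomial gives probability 0.597 for 18/14 or worse and 0.215 for 20/12 or worse. With blocking, both would be rare.

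**The case against.** **The dependent variable and the code may be defined elsewhere.** The SAP says the regression follows a prior crossover trial. The fair statement is therefore that the SAP is not self-contained. The code's two levels are labelled; what is open is which administration they describe.

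**The regression may concern completion.** It follows directly on the completer and attrition text. If so, sequence is a sensible predictor and only its name is wrong. That stands, and it also means the result could not be cited as evidence about the outcomes.

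**A reader might infer that the regression has been shown blind to period.** That goes too far. If the 1/2 code is the current drug and the model includes its interaction with sequence, that interaction is period. The SAP states neither a main-effects model nor an interaction, so the limit holds for the main effects only.

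**A reader might infer that every outcome analysis leaves period out.** The documents do not support this. GEE is the default with its terms unlisted. The SAP also names a chi-square for haemodynamics and alcohol pharmacokinetics, so its chi-square may be a model-based test, including for adverse events. For these analyses the documents are silent. The craving model's water-trial covariate may absorb part of a session shift, and the protocol holds Visits 3 and 5 at the same time of day.

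**The quantified harm is limited.** It reaches one secondary outcome, and only if the t-test is paired. With equal sequences there is no bias and the test is conservative. Averaged over splits from simple randomisation, type I error is 5.0% at every shift. A shift of 1.0 SD is about twice the assumed drug effect. The absence of a randomisation ratio, blocking or numbers per sequence cannot be held against the plan either, since the protocol refers to Appendix Z at randomisation and that appendix is not in the available text.

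**Part of the problem belongs to the design.** No 2×2 crossover can separate carryover from sequence-group differences using cell means. That is not a fault of this SAP, but it is a reason not to claim that carryover was excluded.

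**Conclusion.** The point holds as one of labelling and specification, with a modest analytic consequence. The factor called period is sequence. The available documents do not give the regression's dependent variable or the meaning of its carryover code. The check therefore cannot support a statement that the outcomes are free of period or carryover bias.

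For laboratory drinks, the stated t-test names no period term. If it is paired, the likely cost with near-equal sequences is power and a smaller paired d: slight at a shift of 0.25 SD, material at 1.0 SD. Bias and type I error above 5% appeared only at the 20/12 split among those examined. All shifts and splits are assumptions.

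Two stronger conclusions are tempting and unsupported. The first is that the primary safety comparison is invalid: no consequence for adverse events has been shown, and period there is unstated rather than excluded. The second is that the next trial would be sized wrongly: that depends on its design and analysis, which the documents do not fix. A smaller d would be the right input for a trial that used the same unadjusted paired analysis and met the same shift.

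Severity is minor to moderate. Confidence is high on the label and lower on the consequences.

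**What to change.** - Rename the A/B against B/A factor as sequence. Name the regression's dependent variable, list its terms, and say which administration the 1/2 code describes, in the SAP itself rather than by citation.
- Analyse laboratory drinks with a period-adjusted paired analysis, or with the default GEE containing treatment, period and sequence. Take the effect size from that analysis.
- List the fixed effects of the other mifepristone-against-placebo models and include period: Visit 3 against Visit 5 for laboratory outcomes, and Visit 4 against Visit 6 for follow-up drinking. The motivational session at the end of Visit 5 builds a period difference into the follow-up comparison.
- Say whether the adverse-event chi-square is a table test or a GEE test, and show events by period as well as by drug.
- Report numbers per sequence and the period estimate. Do not cite the logistic check as evidence that the outcomes are free of period or carryover bias, and state that a period term does not remove carryover.

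The cost is SAP wording, a re-run, and one or two degrees of freedom. With no period shift, power for drinks goes from 80.0% to 79.9% at 16/16 and to about 77% at 20/12.

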This study will represent the first intervention of mifepristone on yohimbine-induced alcohol craving and consumption in this population. As this is a safety and tolerability study, adverse events evaluation (AEE) will be reported as the number and their intensity. We will compare the number and intensity of AEE in the mifepristone vs. placebo groups weekly and during the alcohol laboratory sessions. These events will be rated as none, mild, moderate, and severe. Paired *t*-tests will be used to test for medication effects. Generalized Estimating Equations (GEE) will be used for dichotomous data if events are rare. To guard against Type II errors, we will also report additional descriptive data on adverse events (the distribution of the maximum level of an adverse event collapsed across time points per condition). This study integrates self-reported and clinician-administered assessments with clinical laboratory analysis. A series of analyses of covariance (ANCOVA) will be conducted to test the effect of mifepristone on alcohol craving while controlling for variance

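### The SAP tests the primary outcome (number of AEs) and the continuous safety measures of a within-person crossover with an unspecified χ² test, giving neither a paired form nor the unit counted

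*SAP*

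**What the plan says.** The protocol (Overview of Proposed Research) describes a randomized, double-blind, within-person crossover. Its Data analysis section says of AEs: "We will compare the number and intensity of AEE in the mifepristone vs. placebo groups weekly and during the alcohol laboratory sessions". It then plans paired t-tests for medication effects, and GEE for dichotomous data if events are rare.

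The SAP (Primary outcomes) says: "These analyses included comparing the number of adverse events (AEs) between the mifepristone and placebo condition via a" χ² test. The next paragraph adds: "Additional safety and tolerability analysis included hemodynamic response, alcohol pharmacokinetics, and subjective effects of alcohol between the mifepristone and placebo condition", followed by the bracketed label χ² test.

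Four other SAP sentences bear on what that label means:
- The opening paragraph compares enrolled participants with completers using t-tests for continuous variables and Chi square "for categorical variables (e.g., sex, race, smoking status").
- GEE is the default for all analyses, "with robust standard errors, and an unstructured correlation matrix, unless noted".
- Under Secondary outcomes, "In the bar laboratory, alcohol consumption was measured by number of drinks consumed" carries a bracketed t-test label in the same style.
- "The effect sizes were calculated as" η² for GLM and Cohen d for t-tests. No effect measure is named for a χ² comparison.

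**The concern.** Two records from one person are not independent, and a standard Pearson χ² test treats them as if they were. The SAP's Power section justifies the modest sample by the within-subjects design, and an unpaired test on AEs gives that advantage away. In a safety comparison the loss matters, because a non-significant unpaired result could be taken as reassurance.

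The continuous measures raise a second problem. The protocol records heart rate and blood pressure (Cue-reactivity), and repeated breath alcohol values and the Biphasic Alcohol Effects Scale (Alcohol Self-Administration). Neither document defines categories for these, so a Pearson test cannot be applied to them.

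At stake are which p-value is reported for the primary outcome, whether it is calibrated, and whether an estimate of the drug difference accompanies it.

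**Working it through.** **The plan's own figure.** The SAP gives N=32 (raised from 20) with no AE rate, effect size, within-person correlation or power. It cannot be reproduced. It is used below only as the sample size, with two-sided α=0.05 from the SAP. All other inputs are assumptions, so the results are sensitivity figures and not the expected error in this trial.

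**Reading A: Pearson on people with any AE.** With risk p in both conditions and n people, Pearson takes the variance of the difference in proportions as 2p(1−p)/n. If the yes/no outcomes correlate at ρ within person, the variance is 2p(1−p)(1−ρ)/n. The type I error is then approximately P(|Z| > 1.96/√(1−ρ)). At p=0.5, a latent normal correlation r gives ρ = (2/π)·arcsin(r).

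| r | ρ | 1.96/√(1−ρ) | Approximate error | Simulated or enumerated error, n=32 |
|---|---|---|---|---|
| 0 | 0 | 1.96 | 5.0% | 6.0% |
| 0.2 | 0.128 | 2.10 | 3.6% | 4.4% |
| 0.5 | 0.333 | 2.40 | 1.6% | 2.1% |
| 0.7 | 0.494 | 2.75 | 0.6% | 0.8–0.9% |

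The last column is a little higher because the counts are discrete.

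Power was found by enumerating all paired tables at n=32, for any-AE risks of 30% vs 50% (assumed):

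| Within-person correlation ρ | Pearson | Asymptotic McNemar | Exact McNemar |
|---|---|---|---|
| 0 | 0.39 | 0.36 | 0.28 |
| 0.3 | 0.37 | 0.46 | 0.37 |
| 0.5 | 0.34 | 0.62 | 0.49 |

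With no correlation, pairing gains nothing. At 0.5, Pearson loses 0.28 in power against the asymptotic paired test.

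**Reading B: χ² on event totals.** With totals A and B, X² = (A−B)²/(A+B). Suppose counts are Poisson with mean μ per period, a shared person effect (gamma, variance 1) and a person-by-period effect (gamma, variance v). Then Var(A−B) = 2nμ(1+2μv), while the test assumes 2nμ. The inflation factor is 1+2μv, and the error is about P(|Z| > 1.96/√(1+2μv)).

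| μ | v | Factor | Approximate error | Simulated error, n=32 |
|---|---|---|---|---|
| 0.3 or 1 | 0 | 1 | 5.0% | about 5% |
| 0.3 | 0.5 | 1.3 | 8.6% | about 8% |
| 1 | 0.5 | 2.0 | 16.6% | about 16% |

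The shared person effect cancels in the difference, so it does not inflate the error at v=0. Across the wider simulated grid (means 0.3–3, v from 0 to 1), the paired t-test on per-person counts had error of 3.9–4.9%.

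**Reading C: Wald χ² from the default GEE.** Clustering on participant keeps the pairing, and this is the only χ² reading that fits the continuous measures. The SAP does not state it.

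**The case against.** The strongest reply is that one label covers all four measures, and a Wald χ² is the only χ² that suits all four. GEE is the SAP's stated default, and the protocol itself names GEE for rare dichotomous events. On that reading the pairing is kept and the change from the protocol is smaller. This stands as a real possibility, and a reader should not infer that the SAP commits to an unpaired test. It does not settle the matter. The default yields where another method is noted, a test is noted here, and the SAP's only other use of Chi square is an independent-groups comparison of categorical variables. The bracketed t-test for drinks consumed is not labelled paired either, so these labels may simply be shorthand.

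A reader might also infer that ignoring the pairing drives error far above 5%. The calculations do not support that. On people, ignoring positive correlation makes the test conservative. On event totals, the inflation comes from assumed period-specific dispersion. Rates above 40% can be produced (mean 3, dispersion 1), but only with a per-period variance of 3+9×3=30, ten times the mean, and no document supports such a value.

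The consequence is also limited. This is a proof-of-concept pilot with no stated decision rule on the AE p-value. The SAP reports n, means and percentages, and the protocol adds the distribution of maximum AE severity per condition. The SAP's logistic regression for period and carryover is a separate check and does not identify the AE test.

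**Conclusion.** The point holds as a should-fix. For the primary outcome, the SAP names a test whose form and unit cannot be identified, departs without explanation from the protocol's paired test, and attaches the same label to measures a Pearson test cannot handle.

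If Pearson was meant for AEs, error is about 6% falling to about 1% on people (50% risk, latent correlation 0 to 0.7). On event totals it is about 5%, rising to about 8–16% (dispersion 0.5, means 0.3–1). The documents give no AE rate, correlation or dispersion, so neither the direction nor the size for this trial is fixed. If a GEE Wald test was meant, the pairing is respected and the defect is that the plan does not say so.

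On any reading, the primary comparison has no stated estimate of the drug difference. Confidence is medium because the intended χ² is a matter of inference.

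**What to change.** Amend the SAP wording and re-run on existing data:

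1. **Unit.** State whether the primary outcome is AEs per person per condition, people with any AE, or both.
2. **AE counts.** Restore the protocol's paired within-person comparison of per-person counts, reporting the mean difference and 95% CI.
3. **Any AE, if reported.** Use a within-person binary analysis (GEE clustered on participant, or McNemar), with a risk difference and 95% CI.
4. **Hemodynamics, breath alcohol and subjective-effects scores.** Replace the χ² label with a paired comparison of per-session means, or a mixed model or GEE clustered on participant, reporting mean differences and 95% CIs.
5. **Consistency.** Reconcile the SAP's Primary outcomes with the protocol's Data analysis section and give the reason for any change that remains.

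No new participants or procedures are needed. The paired comparison and McNemar drop anyone with only one period, whereas the SAP's ITT set includes people who "received at least one dose of the study medication". A GEE on that set can keep them.
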